### 4. Patient anxiety

Score of HAD scale at 3, 6, 9 and 12 months after inclusion.

### 5. Patient institutionalization and unplanned hospitalizations

- Proportion of patients in nursing home at 6 and 12 months after inclusion.
- Proportion of unplanned hospitalisations during 12 months after inclusion.

### 6. Cost-utility

- Cost-utility ratio at 3, 6, 9 and 12 months
  - Utility assessed through normalised scores of EQ-5D-5L questionnaire collected at baseline, at 3, 6, 9 and 12 months after inclusion. It includes the 5-level questions covering five domains: mobility, self-care, usual activities, pain and discomfort, anxiety and depression.
    - Resource use data during the 12 months of patient follow-up will include all direct and indirect costs. Resource use data directly spurred by patient management collected through the medical-administrative databases of the SNDS (National Health Data System) linked to the patient sample by deterministic matching.

- Cost of hospitalisation;
- Pharmaceutical consumption;
- Outpatient attendance;
- Emergency department access;
- Nursing home care and access to other healthcare facilities;
- Resource use data collected through micro costing
  - Labor costs (salary, over-time, welfare and other compensation);
  - Unpaid caregivers' labor (informal care, community care, or unpaid caregivers' time);
  - Patient or caregiver non-productive leisure time (time that patients or caregiver give up during treatment and convalescence);
  - Time spent by health professionals to manage the patients.

### **7. Caregiver burden in health, psychological well-being, finances, social life and relationship with patient**

Total burden will be obtained using the Zarit Burden Interview [Zarit et al, 1980; Hagell et al 2017] by adding the scores across all 22 items, assessed at baseline, 3, 6, 9 and 12 months after inclusion.

### **8. Patient reported overall experience of person-centered coordinated care**

Patient experience measured through the Person-Centered Coordinated Care Experience Questionnaire (P3CEQ) - 10 items (Lloyd et al 2019) at 6 and 12 months after inclusion.

### **9. Patient, physician and health-professionals-reported overall satisfaction with the IC technology of the GerOnTe system**

Patient satisfaction and usability of mHealth application within GerOnTe system will be analysed through the mHealth App Usability Questionnaire (MAUQ) for standalone mHealth Apps (Patient version), a 21-item scale (Zhou et al 2019) at 6 and 12 months after inclusion.

The adjusted version designed for health care providers of the mHealth App Usability Questionnaire (MAUQ) for standalone mHealth Apps (Provider version), a 21-item scale (Zhou et al 2019) will be used to evaluate physician and health-professional overall satisfaction at 6 months.

### **10. GerOnTe patient-centered system implementation and usage**

GerOnTe patient-centered system implementation and usage will be evaluated at 6 months after inclusion (2 and 4 months for the two last centers implementing GerOnTe system):

- Number and frequency of connections to the Holis™ GV app by patients;
- Duration of logins and activities with the Holis™ GV app by patients;
- Number of web-based meetings with APN by site;
- Number of APN consultations by site (and by patient) and kind of interventions/actions taken;
- Number of PROM's dashboards completed by participant;
- Number of health professional meetings (Multidisciplinary Tumour boards (MTB) or other morbidities treatment decision) involving complete dashboards analysis by site.

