### 4.1. Type of trial

Study design is a stepped wedge randomised controlled trial. Clusters will be participating hospitals, comprising eight investigating sites in total (Figure 2).

This is a stepped wedge of cross-over type. Patients included at each “step” are different individuals. The first “step” is a reference measurement where none of the clusters have implemented the intervention. The investigating sites will be randomly drawn to determine the order in which they will implement the intervention, by “steps” of two months. A total of 10 patients by step are to be included in each center; these 10 patients must be regularly included along the 2-month period of each step. If 10 patients are already included before the end of the 2 months’ step period, the center has to stop the inclusions till the beginning of the subsequent step. If a center, near to the end of a step, is far from reaching the 10 patients included, it must increase the speed of its inclusions to be as close as possible to 10 patients included at the end of the step. In each center, patient sample has to be representative of the type(s) of cancer managed in the center, along the trial duration. The repartition of cancer types must be homogeneous along the steps and during the trial duration.

At all participating investigating sites, dedicated study collaborators will be in charge of organizing intervention implementation and data collection. The intervention will be prepared prior to the start of the trial, so that each investigating site can implement it as defined by the randomisation. Each center committed to participate needs to participate till the end of the trial; no center withdrawal is allowed during the trial.

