#### 4.2. Duration of study (whole population)

The total duration of the study will be approximately 30 months, including 18 months of active enrollment.

Planned start date (first participant on study): September 2022.

The planned study termination (clinical cutoff) corresponds to the date when each participant has been followed-up for 12 months or is deceased.

End of study occurs when all of the following criteria have been satisfied:

- The trial is closed to enrollment

AND

- The last included participant has been followed for 12 months or if deceased, each participant has been followed-up for 12 months or is deceased.

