### 4.3. Definitions of duration of study per participant

Depending on the period (light or dark blue on the figure 2), participants will be included either in the control arm or in the intervention arm.

Participants will be evaluated at scheduled visits as described in section 7.

Each participant will be followed-up for 12 months after inclusion.

If funding permits, a follow-up of patients up to five years after protocol inclusion will be planned. Minimal data will be collected from patient's chart including relapse or progression, survival and institutionalisation.

Participants will be considered to be **on-study** from the signature of the informed consent to the end of follow-up period.

Participants may withdraw their consent at any time; no further study activities will be conducted with them.

**Study discontinuation** occurs when an enrolled participant ceases to participate in the study, regardless of the reason (as detailed under “Follow-up” in Section 7). Participants have the right to withdraw consent at any time; if this is the case, no further follow-up should be performed.

The date and reason for study discontinuation will be clearly documented in the participant’s eCRF.

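### System usage is read at 2 and 4 months in the last two centres, although a 6-month window after inclusion can be observed at all eight sites

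*Protocol*

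**What the plan says.** Section 3.2, item 10 gives the general rule: "GerOnTe patient-centered system implementation and usage will be evaluated at 6 months after inclusion". A parenthesis then makes an exception: "2 and 4 months for the two last centers implementing GerOnTe system". No reason follows. Five of the six measures listed are numbers of events, for example "Number of PROM's dashboards completed by participant". Three of those five are counted by site, one of them also by patient.

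The rest of the protocol sets the time frame:

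- Section 4.1, clusters: "Clusters will be participating hospitals, comprising eight investigating sites in total".
- Section 4.1, roll-out: sites are drawn at random "to determine the order in which they will implement the intervention, by “steps” of two months", one site per step, after a first step in which no site has the intervention.
- Section 4.2: "The total duration of the study will be approximately 30 months, including 18 months of active enrollment". The study ends only when "The last included participant has been followed for 12 months or if deceased, each participant has been followed-up for 12 months or is deceased".
- Section 4.3: "Each participant will be followed-up for 12 months after inclusion".

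Section 4.1 also has app-usage data gathered in every cluster from the moment a site implements the system, and states no early stop.

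**The concern.** The sentence counts time from a patient's inclusion, but the shortened times look like a property of the site: how long it has been running the intervention when recruitment closes. That limits how many intervention patients a late site enrols. It does not limit how long each of them is observed.

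Followed as written, the rule gives cumulative counts over 6 months at six sites, 4 months at one and 2 months at one. Identical behaviour by patients and staff would then produce lower counts at the late sites. Because the order of sites is randomised, the draw would decide which hospitals are affected. Usage is a stated secondary objective (section 2.2), so its by-site description should not carry an artefact that the design does not require.

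**Working it through.** **Inputs.** Enrolment 18 months and study about 30 months (section 4.2); steps of 2 months, eight sites, one switch per step after a common control step (section 4.1); follow-up 12 months per participant (section 4.3); planned intervention patients per site (section 5.1, Table 1).

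**1. Reproduce the 2 and 4 months.** Number of periods = 18 / 2 = 9. With one control period first, the h-th site switches at month 2h, so the time from switch to close of enrolment is 18 − 2h. A patient's 6-month point is the inclusion month plus 6.

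| Site (Table 1 order) | Switch (month) | Switch to close of enrolment | Intervention patients | Patients reach 6 months at study month |
|---|---|---|---|---|
| Hospital 6 | 12 | 18 − 12 = 6 months | 30 | 18 to 24 |
| Hospital 7 | 14 | 18 − 14 = 4 months | 20 | 20 to 24 |
| Hospital 8 | 16 | 18 − 16 = 2 months | 10 | 22 to 24 |

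The protocol's figures come out exactly, and the sixth site has just 6 months, which explains why only two sites carry an exception. The match is an inference; the protocol does not explain the figures. It also does not say which centre has which figure. The arithmetic assigns 4 months to Hospital 7 and 2 months to Hospital 8.

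**2. Is the 6-month window observable there?** The last patient at any site is included by month 18, reaches 6 months by month 24 and completes follow-up at month 18 + 12 = 30. The full window therefore closes about 6 months before the study ends, at every site. Measured from site implementation instead, the time to study end is 30 − 14 = 16 months at Hospital 7 and 30 − 16 = 14 months at Hospital 8. The schedule forces a shorter window on neither reading.

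**3. Consistency with neighbouring items.** Section 3.2, item 8 (care experience) and item 9 (app usability, patient version) are collected at 6 and 12 months, and the provider version of item 9 at 6 months. None has an exception for late centres. As written, patients at the last two sites would rate the app at 6 months while their use of it was evaluated at 4 or 2.

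**4. Size.**

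- Sites affected: 2 / 8 = 25%.
- Intervention patients affected: (20 + 10) / 360 = 8.3%.
- Per-patient count relative to 6 months, if usage is constant over time (assumption): 2 / 6 = 33% and 4 / 6 = 67%.
- Pooled per-patient mean under the same assumption, with equal usage at all sites: (330 × 1 + 20 × 4/6 + 10 × 2/6) / 360 = 346.7 / 360 = 0.963, about 3.7% too low.

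**5. By-site totals.** These also scale with the number of intervention patients, which runs from 10 to 80 per site, up to 80 / 10 = 8-fold. The ratios of 33% and 67% therefore do not describe them, and equal windows alone would not make raw site totals comparable.

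**The case against.** The best defence is that the window was meant at site level. The item concerns implementation as well as usage, some measures are counted by site, and the figures fit the time a site has been active when enrolment closes, capped at 6 months. On that reading the fault lies in the anchor to patient inclusion. This is plausible and stands as an alternative, so the fix must allow for it. It does not rescue the sentence: the anchor would be wrong, and the unequal lengths would still be avoidable (step 2).

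A reader might infer three stronger claims that the documents do not support:

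- *The exception contradicts the follow-up rule.* It does not. Section 4.3 sets how long patients are followed, not when each endpoint is read; the primary endpoint is itself read at 6 months. The follow-up rule only makes the exception unnecessary.
- *The aim of showing organisational fit rests on comparing hospitals by usage.* Section 1.2 speaks of health systems across three countries. No test or ranking of hospitals by usage is specified, and section 4.1 adds a qualitative analysis in each centre.
- *Usage data are lost at the late sites.* Section 4.1 has collection in every cluster from implementation onwards, with no early stop.

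It is also fair to say that one listed measure includes a frequency, and that expressing counts as rates is commonly left to the statistical analysis plan. But the protocol itself fixes the unequal times. If use changes over a patient's first months, rates over 2, 4 and 6 months would still not compare like with like.

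**Conclusion.** The point holds as an avoidable inconsistency in how one secondary endpoint is timed. The exception serves no purpose that the schedule imposes and is tied to the wrong event. It makes cumulative counts at 2 of 8 sites per trial non-comparable with the other six.

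The effect is confined to by-site description. Pooled patient-level summaries move little, because only 8.3% of intervention patients are involved. The ratios of 33% and 67% apply to per-patient counts alone and rest on constant usage. The primary endpoint and the sample size of 720 are unaffected. The conclusion assumes that the planned schedule is kept and that patients can go on using the system after enrolment closes. The protocol nowhere says that the system is withdrawn then, and the app-usability questionnaire at 12 months suggests that it is not.

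**What to change.** In section 3.2, item 10:

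1. Delete the parenthesis and evaluate patient-level usage 6 months from inclusion for intervention patients at all eight sites.
2. For items counted by site, report rates per intervention patient-month, because the number of intervention patients differs so much between sites.
3. If a window starting at site implementation was intended for the by-site items, say so in place of the anchor to inclusion, and apply the same length at every site.

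The cost is a rewording of one item and slightly more analysis work. No extra patients, visits or follow-up are needed. The team should confirm that usage data at the late sites are extracted until about study month 24 and do not stop when enrolment closes.

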## 11. Ancillary studies

Ancillary studies are fully described in Appendix 1 of the protocol.

## 4. Study design

[figure not shown]
### 4.1. Type of trial

Study design is a stepped wedge randomised controlled trial. Clusters will be participating hospitals, comprising eight investigating sites in total (Figure 2).

This is a stepped wedge of cross-over type. Patients included at each “step” are different individuals. The first “step” is a reference measurement where none of the clusters have implemented the intervention. The investigating sites will be randomly drawn to determine the order in which they will implement the intervention, by “steps” of two months. A total of 10 patients by step are to be included in each center; these 10 patients must be regularly included along the 2-month period of each step. If 10 patients are already included before the end of the 2 months’ step period, the center has to stop the inclusions till the beginning of the subsequent step. If a center, near to the end of a step, is far from reaching the 10 patients included, it must increase the speed of its inclusions to be as close as possible to 10 patients included at the end of the step. In each center, patient sample has to be representative of the type(s) of cancer managed in the center, along the trial duration. The repartition of cancer types must be homogeneous along the steps and during the trial duration.

At all participating investigating sites, dedicated study collaborators will be in charge of organizing intervention implementation and data collection. The intervention will be prepared prior to the start of the trial, so that each investigating site can implement it as defined by the randomisation. Each center committed to participate needs to participate till the end of the trial; no center withdrawal is allowed during the trial.

Quantitative data regarding the Holis™ GV home app usage will be collected at each step and in each cluster by study collaborators, from the beginning of GerOnTe system implementation. Care outcome data (Quality of life, anxiety, autonomy, additional hospitalisation, mortality...) will be collected by local referents at 3, 6, 9 and 12 months after inclusion in GerOnTe. The data necessary to calculate the real cost of the intervention, of its implementation and of resource use data of patient management will be continuously collected during follow-up. GerOnTe patient-centered system implementation and usage will be collected by the local referents in each center. Qualitative analysis will be performed in each center at GerOnTe system implementation and during follow-up.

**Figure 2:** Schematic representation of FRONE stepped wedge cross-designed for inclusion of 720 patients across eight sites per trial.

The randomisation list will be established by the statistician at the Methodology and Data Management Centre (EUCLID) prior to the start of the research using SAS software. A document describing the randomisation procedure will be kept confidential within the Methodology and Data Management Centre.

In this stepped wedge trial, the order of integration of the intervention in the sites will be randomised. The intervention will be implemented in a single site at each "step" to ensure optimal power. The centres will be informed at the outset when the intervention will be implemented.

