### 1.2. Rationale

The current work corresponds to deliverable D4.1, which is part of work-package 4 which supports GERONTE objective 3 “Demonstration and validation”. The objective of WP4 is to perform two clinical trials, i.e. FRONE in France and TWOBE in Belgium and the Netherlands, in accordance with ethical and regulatory requirements. The goal is to provide a Proof of Concept of the GerOnTe model in three distinct European countries, and (i) to provide data on how the GerOnTe intervention fits into different health organisation systems, and (ii) to quantify the effectiveness and efficiency of GerOnTe system.

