### 2.2. Secondary objectives

The secondary objectives of GerOnTe trials are, in the context of a French health-system organization for FRONE and in the Belgium and Dutch health-system context for TWOBE, to:

- Evaluate the effectiveness of the GerOnTe patient-centered system to:
  - Improve quality of life at 3, 9 and 12 months (secondary endpoint #1),
  - Improve patient survival and progression-free survival at 12 months (secondary endpoint #2),
  - Improve patient autonomy at 3, 6, 9 and 12 months (secondary endpoint #3),
  - Reduce patient anxiety at 3, 6, 9 and 12 months (secondary endpoint #4),
  - Reduce patient unplanned hospitalizations and patient institutionalizations at 6 and 12 months (secondary endpoint #5);
- Evaluate the efficiency of the GerOnTe patient-centered system through a cost-utility analysis. The medico-economic analysis will focus on the entire care pathway from the beginning of patient management with the GerOnTe system up to 1-year post-inclusion (3, 6, 9 and 12 months after inclusion) (secondary endpoint #6);
- Evaluate caregiver burden in health, psychological well-being, finances, social life and relationship with patient at 3, 6, 9 and 12 months after patient inclusion (secondary endpoint #7);
- Evaluate patient-reported overall experience of the GerOnTe system at 6 and 12 months' post-inclusion (secondary endpoint #8);
- Evaluate patient and health professionals reported overall satisfaction and acceptability of GerOnTe system at 6 and 12 months (secondary endpoint #9);
- Analyze the implementation and use of the GerOnTe patient-centred system by patients and professionals (secondary endpoint #10).
- Ancillary studies

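### No country restriction is stated for TWOBE's switch order, so an unlucky draw could cost precision if time trends differ between Belgium and the Netherlands or results are reported by country

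*Protocol*

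**What the plan says.** Section 4.1 sets out the stepped wedge: "Clusters will be participating hospitals, comprising eight investigating sites in total", and the Figure 2 caption gives "inclusion of 720 patients across eight sites per trial". On the order of switching it says: "The investigating sites will be randomly drawn to determine the order in which they will implement the intervention". One site switches at each step, so there are eight distinct positions. The details are held elsewhere: "A document describing the randomisation procedure will be kept confidential within the Methodology and Data Management Centre".

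Section 1.2 names the two trials as "FRONE in France and TWOBE in Belgium and the Netherlands". TWOBE is therefore one wedge across two health systems. Section 1.2 also gives as a goal "to provide data on how the GerOnTe intervention fits into different health organisation systems", and section 2.2 places the secondary objectives "in the Belgium and Dutch health-system context for TWOBE". The document does not say how many TWOBE sites are in each country, and it mentions no stratification or balancing of the switch order by country.

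**The concern.** A site's position in the wedge decides its mix of patients. In Table 1 (section 5.1) the first site to switch has 10 control and 80 intervention patients; the last has 80 and 10. For FRONE, in one country, a simple random order is unobjectionable. For TWOBE, eight clusters are too few to rely on chance to spread a known two-level factor evenly over the positions.

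If one country's sites cluster in neighbouring positions, there is less contrast between switched and unswitched sites within that country at any given time. This matters in two situations: when time trends over the 18 months of recruitment differ between the countries and the analysis has to allow for that, and when the effect is reported by country. In both, the order of switching affects precision, and it can be controlled at almost no cost before the list is drawn.

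**Working it through.** **Inputs from section 5.1.** Difference 10 points; SD 20; two-sided alpha 1.6%; power 90%; dropout 20%; ICC 0.10; eight sites; 10 patients per site and step. Table 1 gives nine periods (90 patients per site at 10 each).

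**The plan's own sample size.**
- A two-sample t-test with these inputs needs 111 per arm, so 222.
- 222 / 0.80 = 277.5, so 278.
- Stepped-wedge design effect, 8 steps, one baseline period, one measurement per step: [(1 + 0.1 × 89) / (1 + 0.1 × 49)] × [3 × 0.9 / (2 × (8 − 1/8))] = (9.9 / 5.9) × (2.7 / 15.75) = 0.2877.
- 278 × 0.2877 × 9 periods ≈ 720.

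All three figures reproduce. The calculation contains no country term.

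**Assumptions added.** Four sites per country (other splits below) and 10 × 0.80 = 8 evaluable patients per site and period.

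**Imbalance in arm share.** Position p has 10p control and 90 − 10p intervention patients. A country holding positions 1 to 4 has 10 + 20 + 30 + 40 = 100 control and 260 intervention patients, or 72.2% intervention. The other country then has 27.8%. Of the C(8,4) = 70 orders, 34% leave the countries at least 20 percentage points apart, 11% at least 30 points, and 2 of 70 (2.9%) reach the extreme.

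**Precision.** The model for site-period means has a random site effect (variance 0.10 × 400 = 40) and a residual variance of 0.90 × 400 / 8 = 45 per cell, so V = 45·I + 40·J for each site's nine periods. The variance of the effect is its diagonal element in the inverse of the sum over sites of D′V⁻¹D, where D holds the period effects and the intervention indicator. Power = Φ(10/SE − 2.409).

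*Common period effects:* pooled SE 2.66, power 91%, whatever the order of the countries.

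*Country-specific period effects, 4:4 split, all 70 orders:*

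| Order | Within-country SE | Power | Pooled SE | Power |
|---|---|---|---|---|
| Countries alternate | 3.86 | 57% | 2.73 | 90% |
| Median over orders | 4.01 | 53% | 2.85 | 86% |
| Worst (all early / all late) | 4.74 | 38% | 3.35 | 72% |

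With two equally precise countries the pooled SE is the within-country SE divided by √2: 3.86 / 1.414 = 2.73 and 4.74 / 1.414 = 3.35. Pooled power falls below 80% in 6 of the 70 orders (8.6%).

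*Other splits, same model.* At 3:5 the pooled SE is 2.74 at best, 2.86 at the median and 3.29 at worst (power 89%, 86%, 73%). At 2:6 it is 2.76, 2.84 and 3.14 (89%, 87%, 78%).

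**Which feature of the order matters.** Arm share is not a sufficient criterion. A country at positions 3, 4, 5, 6 has exactly half its patients on intervention, yet its SE is 4.74, the same as at positions 1 to 4. At 2:6, positions 4, 5 give a zero gap and SE 9.99, the same as positions 1, 2. At 3:5, positions 4, 5, 6 give an 8.9-point gap and SE 6.29, the worst for any 3:5 order. The spread of a country's positions drives its precision.

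**After a restriction (4:4).** If each consecutive pair of positions holds one site from each country, 16 country patterns remain. Pooled SE lies between 2.73 and 2.77 (power 88% to 90%), the lowest within-country power rises from 38% to 52%, and the share gap is at most 11.1 points.

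**The case against.** A reader might infer that TWOBE's order is drawn without regard to country. The document does not say so. A draw stratified by country would also fit the words of section 4.1, the deliverable calls itself a summary, and the randomisation procedure is kept in a document not seen here. This objection stands, so the point is limited to what is stated. It does not dispose of the matter: a restriction by country can be disclosed without revealing the list, and section 4.1 has centres told their switch date at the outset.

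A reader might also infer that one country could lack a comparison group or that the primary result would be biased. Neither follows. Each site contributes at least 10 patients to each arm, all sites recruit over the same periods, and even the extreme 4:4 order leaves 100 of 360 patients in a country's smaller arm. A random order gives chance imbalance, not systematic bias.

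Next, no country-specific effect is promised. Section 2.2 names the Belgian and Dutch contexts jointly, and the goal about fit with health systems is also served by the usage data and the qualitative work in each centre, which need no balanced order. This stands too. Still, section 1.2 speaks of three distinct countries and of quantifying effectiveness, so results by country are a plausible use of the trial.

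Finally, the usual loss is small. The median order costs about 4% in within-country SE (4.01 against 3.86), and within-country power is only 57% even with alternation. The small number of sites per country is the main limit; the order is secondary.

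**Conclusion.** The point holds in a limited form. The protocol states a random order for eight sites in two countries and no restriction by country; whether the confidential procedure has one cannot be judged from this document. With common period effects nothing is lost. With country-specific period effects and a 4:4 split, the pooled power for 10 points is about 90% if countries alternate, 86% at the median order and 72% at worst, the last with a 2.9% chance. The corresponding within-country SEs are 3.86, 4.01 and 4.74 points. These figures rest on the assumed split, 8 evaluable patients per cell, and the plan's SD and ICC. The 3:5 and 2:6 splits give a similar pattern for the pooled estimate. The documents do not support calling the draw blind to country or the primary comparison confounded. Priority is low to moderate: a modest expected loss with a poor tail, avoidable at almost no cost.

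**What to change.** State the number of TWOBE sites in each country, and randomise the switch order within country with interleaved positions:

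- *Four sites per country:* let each consecutive pair of positions hold one site from each country, with the order inside each pair and the order of sites within country drawn at random.
- *Uneven split:* draw at random from the orders that spread each country's sites across the wedge, for example those whose pooled SE under country-specific period effects is near the minimum. Do not use the gap in intervention share alone.
- *If the confidential procedure already restricts by country:* one sentence in the protocol saying so is enough.

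The cost is a change to the randomisation program before the list is drawn. There are no extra patients or visits, and the total stays at 720. The order becomes slightly more predictable, which matters little because centres learn their switch date at the outset.

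### Unplanned admissions and nursing-home residence rest on referents at sites that know their allocation, although FRONE already plans a database link, stated only for costing, that could serve as source or cross-check

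*Protocol*

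**What the plan says.** - **Source and timing.** Section 4.1 lists the care outcomes, from quality of life to hospitalisation and death, and continues: "additional hospitalisation, mortality...) will be collected by local referents at 3, 6, 9 and 12 months".
- **Who does the work.** At every site, "dedicated study collaborators will be in charge of organizing intervention implementation and data collection" (Section 4.1). Local referents also gather the data on implementation and use of the system.
- **Knowledge of allocation.** "The centres will be informed at the outset when the intervention will be implemented" (Section 4.1). No blinded assessor or adjudication of admissions is described.
- **Extra contacts under the intervention.** Section 3.2, item 10 counts app connections, web meetings with the advanced practice nurse, nurse consultations and completed patient-report dashboards.
- **Endpoint.** Section 3.2, item 5 has unplanned hospitalisations over 12 months and the proportion of patients in a nursing home at 6 and 12 months. Section 2.2 states the aim as a reduction.
- **A second data source.** Section 3.2, item 6 takes resource use over the 12 months from the SNDS, "linked to the patient sample by deterministic matching". The list that follows includes hospitalisation, emergency department access and nursing-home care. It appears only under cost-utility.

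**The concern.** The arm is defined by site and calendar period, so site staff know it for every patient. The intervention consists largely of additional contact between patient and team, and each contact is a chance to learn of an admission elsewhere or a move to a nursing home. Controls lack those channels. If capture is more complete under the intervention, the intervention appears to cause admissions, or a true reduction is hidden. Both work against the stated objective.

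Deciding whether an admission was unplanned adds a judgement, made by people who know the arm.

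FRONE will also hold two records of hospital use: the referents' record for item 5 and the SNDS record for item 6. The document does not say how they relate or which prevails, so the clinical and economic results could disagree about the same admissions. An analysis plan cannot fully repair this if the source and the linkage purpose are not fixed beforehand.

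**Working it through.** The plan gives no admission risk and no capture rate, so there is no stated figure to reproduce. The sample size rests on quality of life and is not touched.

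**Inputs**
- Patients per arm and trial: 10 + 20 + … + 80 = 360 (Section 5.1, Table 1).
- True 12-month risk of an unplanned admission, p, equal in both arms: *assumed* 20% to 40%. The endpoint is read as the proportion of patients with at least one such admission.
- Share of events missed in one arm only, m: *assumed* 0% to 20%. Zero is included because equal capture is possible.

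**Formula**

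With m_C and m_I missed in control and intervention:

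observed difference = p(1 − m_I) − p(1 − m_C) = p(m_C − m_I)

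Only the gap in capture matters. With events missed in one arm only, the size of the spurious difference is p × m.

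**Result (percentage points)**

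| True risk p | m = 0% | m = 5% | m = 10% | m = 20% |
|---|---|---|---|---|
| 20% | 0 | 1.0 | 2.0 | 4.0 |
| 30% | 0 | 1.5 | 3.0 | 6.0 |
| 40% | 0 | 2.0 | 4.0 | 8.0 |

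In patients, 4 points is 0.04 × 360 = 14.4 per arm, and 8 points is 0.08 × 360 = 28.8.

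**Masking example, also assumed.** Let the true risks be 40% in control and 36% under intervention, with 10% of control events missed. Control is observed as 0.40 × 0.90 = 36%. Both arms read 36%, and a 4-point reduction disappears.

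**Does the existing link cover the endpoint?**

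| Needed for item 5 | In the item 6 list? |
|---|---|
| Hospital stays | Yes, as hospitalisation cost |
| Nursing-home entry | Yes, as nursing-home care |
| Planned versus unplanned | Not stated; emergency access is listed |
| TWOBE sites | No database named |

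Death, which Section 4.1 also assigns to the referents, is not in the item 6 list.

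**The case against.** **The bias is assumed.** Referents collect at the same four times in both arms. The document does not say that they rely on patient report rather than hospital records, and it never mentions admissions elsewhere. This stands: equal capture cannot be excluded, which is why the range starts at 0. What remains is that the extra channels come with the intervention itself and nothing described guards against unequal capture.

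**This is a summary, and data sources belong in the full protocol, eCRF or analysis plan.** This stands in part. The document does, however, fix a source for hospitalisation in Section 4.1 and a purpose for the link in item 6. It does not forbid wider use of the link; it is silent.

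**The link does not settle the endpoint.** Also true in part. The document does not show that the SNDS separates planned from unplanned stays. A stay found only there would have no referent report to classify it. A common rule is therefore needed. Equal capture in both arms is a reasonable expectation of an administrative source in FRONE, not something the document states.

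**Stronger readings that the document does not support**
- *Patients who stop visits are lost for these outcomes.* A reader might infer this because study discontinuation "occurs when an enrolled participant ceases to participate in the study, regardless of the reason". But that sentence refers to Section 7 for details, which is not shown. Follow-up is stopped only when consent is withdrawn: "if this is the case, no further follow-up should be performed" (Section 4.3).
- *The 20% dropout means 0.20 × 720 = 144 patients without these outcomes.* The 20% is a sample-size allowance for 6-month quality of life. It may include deaths, which are observed outcomes, and it does not say how many patients withdrew consent.
- *The link would repair the survival endpoint.* Death is not in the item 6 list, and death is little open to observer judgement.

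**Conclusion.** The concern holds as a worthwhile improvement to a secondary endpoint. The described collection leaves room for ascertainment of unplanned hospitalisation and nursing-home residence to differ by arm, and FRONE already plans a data source less dependent on site contact without naming it for this endpoint.

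The size is unknown. Under the assumed risks and capture gaps it is 0 to 8 points, biased against the intervention if controls are the arm with missed events. That staff know the allocation is an inference, though a safe one, from the design and from the advance notice of switch dates. The primary quality-of-life endpoint and the sample size of 720 are not affected.

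**What to change.** **FRONE.** In Section 3.2, item 5 and Section 4.1:
- Name the planned SNDS link as the source for hospital stays and nursing-home entry in both arms, or at least as a prespecified cross-check with a sensitivity analysis.
- State which record prevails when the SNDS and the referents disagree.
- Classify stays as unplanned by one rule applied identically in both arms, not by referent judgement alone. Entry through the emergency department is an example, if the linked data show it. Such a rule would miss unplanned direct admissions, so the sponsor should consider whether the intervention could change the route of entry.
- Use the link for vital status only if it holds it.

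**TWOBE.** No database is named, so specify one record check, identical in both arms. If it uses only the site's own records it will not find admissions elsewhere, and the protocol should say so.

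**Cost.** For FRONE, mainly wording, confirmation that the linkage permission covers this use, and some further analysis of data already being obtained. For TWOBE, the record checks are extra site work. The main downside is that linked data may arrive later than eCRF data.
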